Essential Oils for Enhancing of Quality of Life in Autism Spectrum Disorder (ASD)

[name], PI L. [name], co-PI

INTRODUCTION

Impact and Relevance

Quality of life (QOL) is very often a cause of concern for parents of children with autism spectrum disorder (ASD). This concern may develop as parents observe their children struggle to adapt to the world around them. Children with ASD may become especially agitated when confronted with situations not normally considered challenging for the neurotypical child; and parents of children with ASD learn quickly to avoid potentially volatile situations in order to maintain their child's equilibrium. Comorbid anxiety, with prevalence estimates ranging from 44% to 83% (Johnson et al., 2009; Hollway & Aman, 2011) greatly stresses the ability of the family to engage in enrichment activities. Additionally, anxiety in ASD has been found to be a strong predictor of sleep disturbance (Hollway, Aman, & Butter, 2013) and irregular and delayed sleep may leave the child exhausted, impacting daytime behavior (Meltzer & Mindell, 2006) and QOL in children (Hsiao & Nixon, 2007; Wirell, Blackman, Barlow, Mah & Hamiwka, 2005).

Considerably more impairing, the bidirectional nature of sleep disturbance and anxiety affects QOL, as anxiety may disturb sleep, and a lack of sleep may lead to increased anxiety (Hollway & Aman, 2011). In a report of unpublished data (Hollway, 2012), the investigator found that Emotional Functioning on the Pediatric Quality of Life Inventory (PedsQL) was associated with sleep disturbance in 1583 children with ASD. Out of 12 possible predictors, seven significantly predicted Emotional Functioning [F(7,1482) = 87.643, p < .001]. The results indicated that the Children's Sleep Habits Questionnaire (CSHQ) subscales, Sleep Anxiety, Bedtime Resistance, and being a poor sleeper in general, contributed to quality of emotional functioning and showed a moderate effect ($R^2 = .293$). This indicated that a moderate proportion of the variance found in the PedsQL Emotional Functioning subscale score was explained by the model (29.3%) (Cohen, 1988).

Sleep problems cause significant family distress (Hiscock & Wake, 2002; Doo & Wing, 2006) and clinicians are utilizing behavioral intervention (BI) first for sleep improvement. For many, this intervention is sufficient for improving sleep quality and quantity (Andersen et al., 2008). However, when BI alone is unsuccessful and sleep problems persist, there are few alternatives from which parents can choose that do not involve pharmacological agents (e.g., melatonin, medication) (Hollway & Aman, 2011a; Hollway & Aman, 2011b). As an adjunct, an essential oil formulation distributed by Young Living Essential Oils may be useful for improving quality of life by increasing sleep quantity and equilibrium without the undesirable side effects associated with medications. A pilot study of essential oils will help us determine whether essential oils are tolerable and effective for improving QOL. This study will provide data to help us decide whether continued study is warranted in a much larger multisite study. The proposed research will contribute new knowledge that could be useful for clinicians. The purpose of this research is to increase the existing knowledge regarding quality of life in children with ASD.

Background and Significance

Aromatherapy has been used as a supplement to decrease stress, anxiety, and to help induce sleep (Hur, Song, Lee, J. & Lee, M., 2014; Lee, Wu, Tsang, Leung & Cheung, 2011). However, there is a paucity of empirical data reflecting its effectiveness for improving quality of life in children with sleep disturbances. The data that are available include studies lacking systematic rigor that are fraught with methodological problems (Hirokawa & Nishimoto, 2012; Hur, Song, Lee, J. & Lee, M., 2014; Lee, Wu, Tsang, Leung & Cheung, 2011; Williams, 2006). Studies of late have introduced massage therapy while simultaneously implementing essential oils (Cetinkaya, B., Basbakkal, Z.; 2013; Satou, et al. 2012; Williams, 2006). In these studies the length of the physical contact during the massage may have influenced the study results and it is difficult to tease out whether it was the physical touch during the massage or the aromatherapy that was increasing relaxation and sleep. Other studies have used aromatherapy in a variety of ways such as the diffusion method, applying the oil directly to a body part (without massaging it in), and adding the oil to a cotton ball and attaching it to a piece of clothing (Ndao et al., 2012; Nord & Belew, 2009). In other studies subjects were not randomized (Hirokawa & Nishimoto, 2012), there was not an adequate placebo (Satou et al., 2013), and the sample sizes were quite small (Hirokawa & Nishimoto, 2012; Williams, 2006). Another problem was the subjective nature of the data collection (parent or subject self ratings). Not surprisingly the results were mixed (Jefarzadeh, Arman & Farahbakhish Pour, 2012; Ndao et al., 2012; O'Flaherty, vanDijk, Alertyn & Millar, 2012; Satou et al., 2013; Williams, 2006; Wu, 2014). Our aim is to systematically evaluate in a pilot study the use of Reconnect Essential Oils to determine if it is effective for increasing QOL, equanimity, and sleep. We intend to enroll 28 study participants in a randomized crossover study of Reconnect Essential Oils and a scented coconut oil comparator. Participants will be randomized to two groups. Group 1 will receive Reconnect for the first 3 months of the study while Group 2 will receive a scented coconut oil comparator. At the end of the 3 month period there will be a one month washout and each group will be crossed over to the opposite condition. We will use parent ratings of QOL and objective measures of relaxation/sleep (actigraph).

Specific Aims/Hypotheses

Our primary aims are to evaluate the feasibility of a larger study and examine preliminary data regarding benefit and tolerability of an essential oil formulation distributed by Young Living Essential Oils, Lehi, UT., for enhancing QOL in children with ASDs. We will develop preliminary data suitable to be submitted in a competitive NIH grant application for a larger multisite study. The proposed study will include a 7-month crossover with two 3-month conditions and a month washout between, with randomly assigned order. The 2 conditions will be a proprietary formula of essential oils and a scented coconut oil comparator. Measures of QOL, equanimity, and sleep health will include parent report on valid and reliable rating scales.

Primary Hypotheses

1. We can recruit 28 participants in 2 years with 85% adherence and 85% retention through both conditions.

- 2. With essential oils, participants will show significantly improved QOL on the Pediatric Quality of Life Inventory compared to the control condition, with a medium effect size.
- 3. While receiving essential oils participants will show negligible or no increases in adverse events (AEs), including allergic contact dermatitis, immediate contact reactions (contact urticaria), and photosensitivity, compared to the control condition.

Secondary Mediational Hypotheses

- 1. With essential oils, compared to the control condition, participants will show significantly improved sleep onset and maintenance on objective and subjective measures (actigraphy; parent sleep diaries, and parent and clinician-rated scales) with a medium effect size, and this will mediate the improvement in QOL.
- 2. With essential oils, compared to the control condition, participants will display greater equanimity and improvements in mood and daytime behavior on objective and subjective measures (heart rate; parent and clinician rated scale) compared to the control condition and this will mediate the improvement in QOL.

Participant Inclusion/Exclusion Criteria

Inclusion Criteria

Entry criteria are the following:

- i. Outpatients between 3 and 9 years of age, inclusive;
- ii. Diagnosis of Autism Spectrum Disorder (ASD) by DSM-V;
- iii. Total item mean score of > 1.5 on PedsQL Inventory;
- vi. Care provider who can reliably bring subject to clinic visits and provide trustworthy ratings.

Exclusion Criteria

Exclusion criteria are the following:

- i. Bipolar disorder by Child & Adolescent Symptom Inventory (CASI, Gadow & Sprafkin, 1997) and clinical interview/history, or major depression accompanied by family history of bipolar disorder;
- ii. Children with allergies to essential oils;
- iii. Children with seizure disorder/epilepsy;
- iv. Significant physical illness (e.g., serious cardiovascular, liver, or renal pathology);
- v. Medications specifically given for insomnia and exogenous melatonin, which have the potential to confound study results, within the previous 2 weeks before baseline;
- vi. Anticipated changes of doses of medication or other medical treatments or supplements;
- vii. Weight less than 10 kg;
- viii. Sleep Disordered Breathing (SDB) as defined by a total score of ≥ 3 on the CSHQ SDB subscale and parent report;
- ix. Nut allergies;
- x. Allergy to vanilla;
- xi. A substantial trial of essential oil use within the past 6 months (i.e., consistent use for 6 weeks).

METHODS

Study Design

This study will use a double-blind -controlled crossover design with random assignment to order of conditions. The 2 conditions will be ReconnectTM, a mixture of essential oils formulated by Young Living (YL) vs. a fragrant appearance-matched coconut-oil comparator. In order to randomize 28 children we anticipate that approximately 36 children will be screened. There will 2 conditions in the crossover design.

Participants will receive Reconnect or scented coconut oil comparator for 3 months following the Baseline visit. At the end of 3 months, participants will be administered all endpoint measures for that condition. Then there will be a 1-month washout prior to the start of the second condition. At the end of the second 3-month condition, participants will again be administered all endpoint measures for that condition. The endpoint assessment for the 2nd condition will be 7 months from original baseline. During the 1st condition participants will be evaluated at 2 week intervals for the first month to assess whether the mode of essential oils application is tolerable (i.e., inhalation or topical application) and to develop graphs of effect on sleep and equanimity over time. During the final 8 weeks of condition one, participants will be seen monthly. During the second condition we will have established that the modes of application are tolerable and subjects will be evaluated at 3 monthly visits. There will be 10 visits to the Center including the Screening and Baseline Visits.

Procedures

All participants must have significant problems with QOL as measured by the PedsQL Inventory, with a total item mean score of ≥ 1.5 (i.e., one standard deviation below the normative mean).

At baseline, participants will be randomly assigned to one of two orders of essential oils. The oil will be dispensed at the Baseline visit, and will be administered by both massaging the oil on the feet and the back of the neck in the morning and by the diffusion method in the evening.

In this study, clinical responders will be defined as showing a 30% improvement in the total score of the PedsQL Inventory.

Approximately 50% of children will wear a device known as an actigraph that measures activity level and sleep quality. There will be 6 actigraphs and they will be assigned to participants as they are made available on a first come first serve basis. There may be some participants who are unwilling to wear the actigraph and for those who are tactiley defensive we will not require them to do so. Participants will wear the devices for five consecutive nights, on three separate occasions (i.e., between Screening and Baseline, prior to the End Point of the first 3 month period, and prior to the End Point of the second 3 month period). The small watch-like devices worn on the wrist or ankle will collect activity data and measure body temperature while the participant sleeps. They will yield the following sleep variables: 1) time in bed, 2) total sleep time (from lights out), 3) sleep onset latency, 4) morning waking time, 5) frequency of night

wakings, 6) longest sleep period, and 7) sleep efficiency. This is a reliable method of objective data collection for sleep-wake patterns including timing, continuity, and duration of sleep.

In the proposed study, there will be a primary clinician (the physician) and an independent evaluator. The physician will discuss possible side effects and make dose or administration mode adjustments. The independent evaluator will interview the parents with respect to target improvements (QOL) and make DD-CGAS ratings based on all feedback, including parent rating scales.

Dosing

Each participant will utilize both oil delivery methods: diffusion at night and topical application in the morning. If a participant is unable to tolerate one of these delivery methods, then both the morning and night-time doses can be administered via the same, more tolerable method.

ReconnectTM Directions:

To be applied only by a trusted adult or under adult supervision.

Topical: Apply 1 drop to the back of the neck and 1 drop to the feet. Rub in the oil for 30 seconds to 1 minute. Each bottle has an orifice that allows the oil to be expelled drop by drop. Dilution is not required, except for the most sensitive skin. Apply in the morning.

Aromatic Method: Diffuse one diffuser-full (8-12 drops of oil in water) at night.

- 1. Home diffuser instructions: Open the water reservoir by lifting the lid. Add room-temperature water (distilled water is recommended) up to the fill line of the reservoir. Do not exceed the fill line.
- 2. Add 8-12 drops of Reconnect to the water.
- 3. Replace the lid to cover the water reservoir.
- 4. Plug in the Home Diffuser and push the power switch to start diffusing.
- 5. When water runs out, the diffuser will automatically shut off.
- 6. To cycle through the three-mode power settings, press the power switch quickly: Mode 1: Green light Constant diffusion Mode 2: Red light 30 seconds intermittent diffusion Mode 3: Off. Use constant diffusion (green light, mode 1).
- 7. To turn on/off the ambient LED light, press and hold the power switch for approximately 2 seconds.

Notice: Due to the mist output of the Home Diffuser, use caution on surfaces that are sensitive to water.

Essential Oil

The type of Young Living essential oil we will be utilizing is ReconnectTM. ReconnectTM contains the following ingredients: Caprylic/capric triglycerides, Prunus amygdalus dulcis (Sweet almond) oil, Boswellia sacra† oil, Citrus aurantium bergamia† peel oil, Commiphora myrrha oil, Lavandula angustifolia† oil, Pelargonium graveolens† flower oil, Callitris intratropica wood oil, Santalum paniculatum† wood oil, Cananga odorata† flower oil, Cedrus atlantica† wood oil, Aniba rosaeodora† wood oil, Melissa officinalis† leaf oil, Picea pungeons†

branch/leaf/wood oil, Picea mariana leaf oil, Hyssopus officinalis† leaf oil, Rosa damascena† flower oil. The comparison oil is coconut oil with a tiny amount of vanilla, just enough for an aroma. Please see Table 2 for a listing of the ingredients, their current common uses, and potential side effects.

Primary Outcome Measure

Pediatric Quality of Life Inventory (PedsQL) (Varni, Burwinkle, & Seid, 2006). The 23-item PedsQL Generic Core Scales were designed to measure the core domains of health and their impact on the quality of life in children as outlined by the World Health Organization. The four Multidimensional Scales are: Physical Functioning, Emotional Functioning, Social Functioning, and School Functioning. The summary scores include a Total Scale Score, a Physical Health Summary Score, and a Psychosocial Health Summary Score. Response choices are in Likert-scale format ranging from 0 to 4 (i.e., 0 = Never, 1 = Almost Never, 2 = Sometimes, 3 = Often, 4 = Almost Always). There are 4 versions of the PedsQL including versions for ages 2-4 years, 7 years, 8-12 years, and 13-18 years. We will use the age-normed scale for each child that matches the age the child is expected to be at the end of the first condition; once selected, the same scale will be used throughout that child's participation. To be enrolled participants will have clinically significant problems with quality of life (i.e., total item mean score of ≥ 1.5).

Other Measures for Establishing Study Inclusion Criteria

Autism Diagnostic Observation Schedule (ADOS) (Rutter et al., 2004). The ADOS is an investigator-based assessment that places the child in naturalistic social situations demanding specific social and communication responses. Behaviors are coded in the areas of social communication, social relatedness, play and imagination, and repetitive behaviors. The ADOS provides a DSM- based algorithm for the diagnosis of ASD. The ADOS will be administered by a research-reliable clinician if it has not already been done by a reliable administrator.

Child and Adolescent Symptom Inventory (CASI) (Gadow & Sprafkin, 2004). We will use the CASI to evaluate children ages 3 to 9 years of age for symptoms of common childhood psychiatric disorders. The CASI will aid ruling out exclusionary psychiatric disorders. Based on DSM-IV diagnostic criteria, this scale assists clinicians by providing useful diagnostic information from parents. The inventory offers both criterion-related cut-off scores and normbased scores for determining symptom severity (low, moderate, or high, based on parent ratings.

Exploratory Dependent Measures in addition to PedsQL

Developmental Disabilities – Children's Global Assessment Scale (DD-CGAS) (Wagner et al., 2007). The DD-CGAS is a reliable instrument for measuring global functioning of children with developmental disorders in treatment studies. We will use the DD-CGAS to characterize children's impairment on the following four domains: Self Care, Communication, Social Behavior, and School/Academic. In addition, this scale also includes a series of descriptive "bands" to characterize global functioning in children with pervasive developmental disorders from "extreme and pervasive impairment" through "superior functioning."

Parent Stress Index (PSI) (Abidin, 1995). The PSI is used to evaluate the degree of stress in the

parent-child relationship. The Short Form is composed of 36 items taken from the full length PSI and is completed in 10-15 minutes. Child characteristics in the full scale include Distractibility/Hyperactivity, Adaptability, Reinforces Parent, Demandingness, Mood, and Acceptability. Parent measures include Competence, Isolation, Attachment, Health, Role Restriction, Depression, and Spouse. The PSI is used for early identification of dysfunctional parent-child interactions, parental stress, and family functioning. It may be used for parents of children up to 12 years, but it is primarily intended for parents of children 0-3 years. It yields a Total Score and three domain scores. Parents rate each of the 36 items on a 5-point scale (1 = strongly disagree, to 5 = strongly agree). The 90^{th} percentile of the Total PSI score represents a clinically significant level of parenting stress (i.e., total score of ≥ 260). The PSI will be a secondary outcome.

Children's Sleep Habits Questionnaire (CSHQ) (Owens, Spirito, & Mcguinn, 2000). The abbreviated CSHQ is a valid measure of sleep problems with good psychometric properties. The CSHQ was designed for use in children 3 to 7 years of age. It includes 33 items and is rated retrospectively over the previous week by parents to screen for the most common sleep problems. The CSHQ incorporates items related to eight key sleep domains. The eight subscales include: (1) bedtime resistance (2) sleep onset latency, (3) sleep duration, (4) anxiety around sleep, (5) night awakenings, (6) sleep disordered breathing, (7) parasomnias and (8) morning waking/daytime sleepiness. A Total Score of 41 or greater on the CSHQ 33 items has been reported to be an appropriate clinical cut-off for identifying sleep problems in children. In a recent study of the participants in the Autism Treatment Network 75% of the participants analyzed had a CSHQ score of 41 or higher (Hollway, Aman, and Butter, 2013). The Abbreviated CSHQ will be used to determine whether a child has a clinically significant sleep problem and will be a secondary (mediational) outcome measure of the study.

Parent Sleep Diary (Thomas & Burr, 2009). A parent/caregiver diary documenting overall information about participant sleep-wake behavior patterns, will be implemented. Caregivers will record "time in bed," time asleep," "time awake after sleep onset," and "number of nighttime awakenings." The diary will be used in conjunction with the CSHQ rating scale to collect caregiver estimates of sleep efficiency. These data will be evaluated for their reliability when compared to our objective measure of the sleep, the Motion-logger Micro Watch. The sleep diary will be distributed to the caregiver at the end of each visit to be filled in at home each morning.

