Demographic and recruitment information will be summarized. Frequency tables will be used to summarize toxicity and tolerability based on type, severity, and attribution of the adverse events during each condition. Clinical outcomes will be plotted and summarized for all subjects over time by individual and condition. Data summaries for missing and outlying data will be distributed and reviewed. Visual displays will be generated and presented to investigators in order to identify any outliers or other problems that could be missed by summary statistics. The categorical outcomes will be tabulated for each condition. The effect sizes of the changes of these clinical outcomes after 12 weeks will be estimated, using Cohen's definition, for each condition. Each phase will last for a total of 12 weeks. The effect size of active vs control condition will be calculated as the differences of the mean improvements between conditions, divided by pooled standard deviation of the improvements from the two groups.

Sample size and Randomization

This randomized crossover pilot study will have 28 subjects randomized into 2 orders of condition with a block size of 4 initially, then block size of 2 as the sample size nears

[figure not shown]
completion. Considering up to 15% early drop outs due to reasons not related to essential oils, we plan to randomize up to 33 subjects.

With 28 participants in this crossover study and using the participants as their own controls we estimate that we will be able to detect statistical significance with an effect size of **0.8.** In addition, we will compare the changes of the clinical outcome variables between Reconnect and control conditions by testing the interaction of condition and time based on a linear mixed model for repeated measurement, with conventional alpha of 0.05 for the primary outcome. In order to protect against Type 2 error in this pilot study, we will not correct for multiple tests.

Study Time Line

Study Timeline. The time-line for the study appears in Figure 1. The first several months will be used to obtain IRB approvals and create Case Report Forms or source documents. The next 19 months will be used for participant recruitment, supplementation, and assessment. Finally, the last 3 months will involve data analysis and manuscript writing.

Table 3. Study Timeline (24 months)

REFERENCES

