				colophony and propolis as screening tools in the detection of fragrance allergy. British Journal of Dermatology, 145: 268–273. doi: 10.1046/j.1365-2133.2001.04345.x Hausen BM. Contact allergy to balsam of Peru. II. Patch test results in 102 patients with selected balsam of Peru constituents. Am J Contact Dermat. 2001;12(2):93–102. [PubMed]
Coconut Oil	Used as a flavoring in foods. Added to some pharmaceuticals and cosmetics. Commonly rubbed on the skin.	Populations of people that consume large quantities of coconut oil show no adverse effects. According to the FDA, "There is no evidence in the available information on coconut oil, peanut oil, and oleic acid that demonstrates, or suggests reasonable grounds to suspect, a hazard to the public as they are now used in paper and cotton packaging material for food at levels now current or as they might reasonably be expected to be used for such purposes in the future."	Composed of 92% saturated fatty oils.	Thampan, P.K., Glimpses of coconut industry in India, Coconut Development Board, Cochin 1988. Krishna, G., Rah, G., Bhatnagar, A. S., Kumar, P., & Chandrashekar, P. Indian Coconut Journal. "Coconut Oil: Chemistry, Production and Its Applications - A Review." 2010. "Select Committee on GRAS Substances (SCOGS) Opinion: Coconut Oil (packaging)." U.S. Food and Drug Administration, Apr. 2013. Web. 02 Jan. 2015.

Human Subjects considerations

Participants:

Participants are 28 children age 3-9 with autism spectrum disorder and excessive anxiety and sleep disturbance. Although we are not treating autism, this population is especially prone to impaired QOL due to sleep problems and anxiety, and is the population for which OTC essential oils are most often used by consumers without adequate test of benefits and safety. Careful evaluation of this practice has been requested by parents of children with autism.

Risks:

Essential oils themselves are generally regarded as safe and are routinely used by the public. One of the purposes of this pilot study is to check whether this assumption is valid. The main known risk/discomfort is from the blood draws, with possible bleeding, bruising, or infection. The ratings pose some time/effort burden for parents and the usual confidentiality risks apply. Although uncommon, skin irritation with topical administration or breast enlargement in boys is a potential side effect of a few ingredients of Reconnect (See Table 2).

Minimization of risk:

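### Primary Hypothesis 3 predicts a negligible increase in adverse events, but the planned per-condition tables do not show how large an increase remains possible when the counts look alike

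*Combined protocol and SAP*

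**What the plan says.** Under Primary Hypotheses, item 3 predicts that "participants will show negligible or no increases in adverse events (AEs"). It names the reactions of interest and makes the claim comparative: "allergic contact dermatitis, immediate contact reactions (contact urticaria), and photosensitivity, compared to the control condition". No threshold for negligible is given.

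The Data Analytic Plan lists safety among the three parts of the pilot's primary goal. The Risks paragraph of Human Subjects considerations notes that essential oils are generally regarded as safe and adds: "One of the purposes of this pilot study is to check whether this assumption is valid".

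The one sentence on analysing AEs is in the Data Analytic Plan: "Frequency tables will be used to summarize toxicity and tolerability based on type, severity, and attribution of the adverse events during each condition". The same section says in general terms that the analysis will mainly compare Reconnect with control, but it gives no difference, interval or use of the within-child pairing for AEs. Under Sample size and Randomization, the mixed model is for the clinical outcome variables and the alpha of 0.05 is for the primary outcome, which is quality of life. On numbers, that section says "This randomized crossover pilot study will have 28 subjects randomized into 2 orders of condition", and then "Considering up to 15% early drop outs due to reasons not related to essential oils", "we plan to randomize up to 33 subjects".

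**The concern.** A hypothesis of little or no increase is supported only when a meaningful increase has been made unlikely. Similar counts in two columns of a small table do not do that, because the same counts can arise when the true rates differ by a good deal. The plan has a comparative primary hypothesis about AEs and no stated way to express the uncertainty of that comparison. It also makes no stated use of the crossover's pairing.

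The participants are aged 3 to 9, checking safety is a declared purpose, and the pilot data are meant for a grant application for a larger multisite study. A reader of that application would want to know what size of AE increase the pilot had and had not ruled out.

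**Working it through.** **Inputs from the documents.** 28 children, two conditions each; dropout allowance 15%; up to 33 randomised; retention target 85% through both conditions. The documents give no AE rate and no margin.

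**The plan's own figure.** 28 / (1 − 0.15) = 32.94, rounded up to 33, which agrees. If 33 are randomised and 85% complete, 33 × 0.85 = 28.05, so about 28 have both conditions. If only 28 are randomised, 28 × 0.85 = 23.8, so about 24. Both numbers are used below.

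**Paired difference.** Let b be the number of children with an event on Reconnect only, c the number on control only, and n the number exposed to both. The difference is (b − c)/n. The two-sided 95% Tango score limits are the values Δ that satisfy

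|b − c − nΔ| / √{n[2q + Δ(1 − Δ)]} = 1.96,

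where q = [√(B² − 4AC) − B]/(2A), A = 2n, B = −b − c + (2n − b + c)Δ and C = −cΔ(1 − Δ).

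*No discordant child (b = c = 0).* Here q = 0, and the upper limit reduces to z²/(n + z²), with z² = 3.84:
- n = 28: 3.84/31.84 = 12.1 points
- n = 24: 3.84/27.84 = 13.8 points

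Cross-check with an exact bound: the difference cannot exceed the probability of an event on Reconnect only. For 0 of 28, the exact 97.5% upper bound on that probability is 1 − 0.025^(1/28) = 12.3%.

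*One child each way (b = c = 1), n = 28.* At Δ = 0.149, B = 6.344, C = −0.1268 and q = 0.0173. The variance term is 28 × (0.0347 + 0.1268) = 4.52, and 28 × 0.149/√4.52 = 1.96. The upper limit is therefore 14.9 points. The other cells are solved in the same way.

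| Exposed to both | 0 v 0 | 1 v 1 | 2 v 2 |
|---|---|---|---|
| 28 | +12.1 | +14.9 | +17.2 |
| 24 | +13.8 | +17.0 | +19.7 |

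The observed difference is zero in every cell.

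**How often the tables would look reassuring.** This step needs assumed rates. Take 5% on control and 15% on Reconnect, a true excess of 10 points, independent within child. The chance of an event on Reconnect only is 0.15 × 0.95 = 0.1425, and on control only 0.05 × 0.85 = 0.0425. Summing the trinomial probabilities for n = 28, the tables show an excess of at most one child 28% of the time, and no excess at all 14.5% of the time. With 10% v 20% the figures are 31% and 19%. With 24 children and 5% v 15% they are 33% and 17%.

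**The case against.** This is a pilot, and the aims call its benefit and tolerability data preliminary. Descriptive AE tables are a normal pilot summary, and an expectation listed as a hypothesis is not a decision rule. That stands, and it is why the tables should be kept and no larger sample is asked for.

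A reader might infer that the plan would let a sizeable excess be reported as negligible. The documents do not support that. Events are tabulated by type, severity and attribution in each condition, so five children affected on Reconnect only and none on control only, an 18-point excess, would be plain to see. Nor does any section give a rule for accepting Hypothesis 3, or say that a claim of negligible harm will go into the grant application. The gap is narrower: nothing shows the uncertainty when the counts are close.

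A reader might also summarise the limit by saying that zero events in 28 children leaves a rate of up to 10.1% (one-sided 95%) or 12.3% (two-sided) possible. That is a rate in one condition, while the hypothesis concerns an increase over control. It also fixes the denominator at 28, when the number exposed could be anything from about 24 to 33.

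A last objection has force. A strictly within-child difference leaves out a child who stops in the first period because of an AE, who is among the most informative cases for safety. The fix has to deal with this.

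**Conclusion.** The point holds in a limited form. The stated AE analysis cannot support the stated primary hypothesis, because it gives no measure of how large an increase is still possible. With no observed difference, that increase is about 12 to 17 points with 28 children in both conditions and about 14 to 20 with 24. The ranges cover zero to two discordant children in each direction and use score limits; the exact bound for the 0 v 0 case is almost the same. They need no assumption about AE rates. The probabilities of a reassuring table do, because the documents give no rates, and they are only illustrations.

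The trial's validity is not in question. What changes is the strength of the safety statement it can make. That is worth correcting before the data are analysed, since safety is a primary goal and the correction is cheap.

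**What to change.** Keep the frequency tables and add the following to the Data Analytic Plan.

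1. For any AE, and for each named skin reaction, report the Reconnect-minus-control difference in the proportion of children with at least one event, with a 95% confidence interval.
2. Base each condition's proportion on all children exposed to that condition, so that those who stop in the first period are counted. Give the paired difference for children exposed to both conditions alongside.
3. Name the interval method in advance, because methods can disagree at these counts. For 5 v 0 among 28, the score interval is +3.6 to +35.6 points, while the exact McNemar p-value is 2 × 0.5⁵ = 0.0625.
4. State how events recorded at the week 16 visit, which closes the washout, are assigned to a condition.
5. Reword Hypothesis 3 as estimating the increase in AEs. State that no claim of a negligible increase will go beyond the upper confidence limit, calculated from the number actually exposed. No margin has to be invented.

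The cost is slightly more analysis of data already collected at the scheduled visits, with no new visits or participants. The intervals for rare reactions will be wide, and the safety statement will be less favourable than the present wording anticipates.
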